| Serum creatinine >2.5 mg/dL (221 umol/L)                                                                                                                                                                                                                                                                                   | Measured 180 days prior to and including the day of drug initiation in any diagnosis position and in an inpatient or an outpatient care setting

CKD, ESRD:
ICD-9 Dx:
585.4x, 585.5x, 585.6x: CKD 4, 5, ESRD
586.xx: renal failure

ICD-10 Dx:
N19.xx
N18.4x Chronic kidney disease, stage 4 (severe)
N18.5x Chronic kidney disease, stage 5
N18.6x End stage renal disease
N18.9x Chronic kidney disease, unspecified |  |  |
| Calculated creatinine clearance <25 ml/min                                                                                                                                                                                                                                                                                 |                                                                                                                                                                                                                                                                                                                                                                                                                                                                   |  |  |
| ALT or AST >2 times upper limit of normal                                                                                                                                                                                                                                                                                  | N/A
(Incorporated into moderate/severe liver disease above)                                                                                                                                                                                                                                                                                                                                                                                                    |  |  |

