# Appendix B

|                                                                |             |               |       |               |               |       |               |               |         |              |              |         |
|----------------------------------------------------------------|-------------|---------------|-------|---------------|---------------|-------|---------------|---------------|---------|--------------|--------------|---------|
| Chronic kidney disease v2; n (%)                               | 80 (5.4%)   | 116 (4.2%)    | 0.06  | 76 (3.1%)     | 102 (2.6%)    | 0.03  | 345 (6.9%)    | 189 (5.5%)    | 0.06    | 501 (5.6%)   | 407 (4.0%)   | 0.07    |
| CKD Stage 3-4; n (%)                                           | 48 (3.3%)   | 90 (3.2%)     | 0.01  | 56 (2.3%)     | 75 (1.9%)     | 0.03  | 249 (5.0%)    | 143 (4.2%)    | 0.04    | 353 (4.0%)   | 308 (3.1%)   | 0.05    |
| Occurrence of hypertensive nephropathy; n (%)                  | 41 (2.8%)   | 51 (1.8%)     | 0.07  | 53 (2.2%)     | 69 (1.8%)     | 0.03  | 213 (4.3%)    | 98 (2.9%)     | 0.08    | 307 (3.4%)   | 218 (2.2%)   | 0.07    |
| Occurrence of miscellaneous renal insufficiency v2; n (%)      | 92 (6.2%)   | 163 (5.9%)    | 0.01  | 132 (5.4%)    | 192 (5.0%)    | 0.02  | 326 (6.5%)    | 229 (6.7%)    | -0.01   | 550 (6.2%)   | 584 (5.8%)   | 0.02    |
| Other Covariates                                        |             |               |       |               |               |       |               |               |         |              |              |         |
| Liver disease; n (%)                                           | ** (0.5%)   | ** (0.1%)     | 0.07  | 0 (0.0%)      | ** (0.1%)     | -0.04 | 28 (0.6%)     | ** (0.2%)     | 0.06    | #VALUE!      | #VALUE!      | #VALUE! |
| Osteoarthritis; n (%)                                          | 283 (19.2%) | 553 (19.9%)   | -0.02 | 397 (16.1%)   | 570 (14.7%)   | 0.04  | 1,164 (23.4%) | 836 (24.5%)   | -0.03   | 1844 (20.7%) | 1959 (19.5%) | 0.03    |
| Other arthritis, arthropathies and musculoskeletal pain; n (%) | 868 (59.0%) | 1,587 (57.0%) | 0.04  | 1,414 (57.4%) | 2,100 (54.2%) | 0.06  | 2,917 (58.5%) | 1,938 (56.9%) | 0.03    | 5199 (58.3%) | 5625 (55.9%) | 0.05    |

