| Occurrence of creatinine tests ordered (for PS); n (%)                                     | 82 (5.6%)     | 194 (7.0%)    | -0.06   | 147 (6.0%)    | 199 (5.1%)    | 0.04    | 430 (8.6%)    | 286 (8.4%)    | 0.01      | 659 (7.4%)    | 679 (6.7%)    | 0.03    |
| Occurrence of BUN tests ordered (for PS); n (%)                                            | 33 (2.2%)     | 81 (2.9%)     | -0.04   | 76 (3.1%)     | 103 (2.7%)    | 0.02    | 225 (4.5%)    | 151 (4.4%)    | 0.00      | 334 (3.7%)    | 335 (3.3%)    | 0.02    |
| Occurrence of chronic renal insufficiency w/o CKD (for PS); v2; n (%)                      | 18 (1.2%)     | 13 (0.5%)     | 0.08    | 23 (0.9%)     | 16 (0.4%)     | 0.06    | 102 (2.0%)    | 32 (0.9%)     | 0.09      | 143 (1.6%)    | 61 (0.6%)     | 0.10    |
| Chronic kidney disease Stage 1-2 (for PS); n (%)                                           | 27 (1.8%)     | 28 (1.0%)     | 0.07    | 18 (0.7%)     | 29 (0.7%)     | 0.00    | 0             | 0             | #VALUE!   | #VALUE!       | #VALUE!       |         |
| Chronic kidney disease Stage 3-6 (for PS); n (%)                                           | 48 (3.3%)     | 90 (3.2%)     | 0.01    | 56 (2.3%)     | 75 (1.9%)     | 0.03    | 249 (5.0%)    | 143 (4.2%)    | 0.04      | 353 (4.0%)    | 308 (3.1%)    | 0.05    |
| Acute kidney injury; n (%)                                                                 | 86 (5.8%)     | 204 (7.3%)    | #DIV/0! | 159 (6.5%)    | 264 (6.8%)    | #DIV/0! | 0 (0.0%)      | 0 (0.0%)      | #DIV/0!   | 159 (6.5%)    | 264 (6.8%)    | 0.37    |
| Bladder stones+Kidney stones (for PS); n (%)                                               | 58 (3.9%)     | 111 (4.0%)    | -0.01   | 69 (2.8%)     | 118 (3.0%)    | -0.01   | 177 (3.6%)    | 117 (3.4%)    | 0.01      | 304 (3.4%)    | 346 (3.4%)    | 0.00    |
| Alcohol abuse or dependence+Drug abuse or dependence (for PS); n (%)                       | 93 (6.3%)     | 210 (7.5%)    | -0.05   | 77 (3.1%)     | 126 (3.3%)    | -0.01   | 387 (7.8%)    | 279 (8.2%)    | -0.01     | 557 (6.2%)    | 615 (6.1%)    | 0.00    |
| Other atherosclerosis+Cardiac conduction disorders+Other CVD (for PS); v2 Copy; n (%)      | 459 (31.2%)   | 916 (32.9%)   | -0.04   | 670 (27.2%)   | 1,136 (29.3%) | -0.05   | 1,423 (28.6%) | 1,010 (29.7%) | -0.02     | 2552 (28.6%)  | 3062 (30.4%)  | -0.04   |

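### The renal exclusion includes unspecified CKD in ICD-10 but not in ICD-9, so it differs by coding system and reaches beyond the trial's renal limits

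*Combined protocol and SAP*

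**What the plan says.** In the exclusion criteria of Appendix A, one code cell stands in for two laboratory limits of the trial: "Serum creatinine >2.5 mg/dL (221 umol/L") and "Calculated creatinine clearance <25 ml/min". The look-back is 180 days up to and including drug initiation, with any diagnosis position, inpatient or outpatient.

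The ICD-9 list is "585.4x, 585.5x, 585.6x: CKD 4, 5, ESRD" together with "586.xx: renal failure". The ICD-10 list is N19.xx (printed without a label), "N18.4x Chronic kidney disease, stage 4 (severe"), N18.5x (stage 5), N18.6x (ESRD) and "N18.9x Chronic kidney disease, unspecified".

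Section 5.2.2 says the criteria were kept as near to the trial's as the data allow. Appendix A adds that ICD-10 lists were derived from ICD-9 by a forward/backward mapping macro and that the full lists sit in an external folder. No reason is given for the extra ICD-10 category. In Section 5.3, exclusion # 18 (CKD/ESRD) shares one flowchart line with # 17 (anemia) and # 22 (heparin-induced thrombocytopenia).

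**The concern.** There are two separate faults. The first is consistency: the same exclusion should mean the same thing whichever coding system recorded the diagnosis, and here it does not. The second is fidelity: the trial excluded severe renal impairment, and a code that states no stage is not evidence of creatinine above 2.5 mg/dL or clearance below 25 ml/min.

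Renal function bears on bleeding risk, and major bleeding is the safety outcome. A rule that removes some patients within the trial's renal limits, and does so under only one coding system, moves the cohort away from the trial population for no stated reason. Matching cannot repair this, because excluded patients never reach the propensity score.

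**Working it through.** **1. The two lists side by side, using the plan's own labels.**

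| Category | ICD-9 list | ICD-10 list |
|---|---|---|
| CKD stage 4 | 585.4x | N18.4x |
| CKD stage 5 | 585.5x | N18.5x |
| ESRD | 585.6x | N18.6x |
| Renal failure | 586.xx | N19.xx (unlabelled; taken as the counterpart) |
| CKD, unspecified | none | N18.9x |

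ICD-10 minus ICD-9 leaves unspecified CKD. ICD-9 minus ICD-10 leaves nothing. Pairing N19.xx with 586.xx is an assumption, but the result for N18.9x does not depend on it.

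**2. What this does to a patient.** Take someone whose only renal code in the look-back is unspecified CKD. Under the ICD-9 list no code matches and the patient stays. Under the ICD-10 list N18.9x matches and the patient goes. Nothing about renal function differs.

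**3. Whether both systems are in play.** Section 5.2.1 opens entry on August 21, 2014 and closes it at the end of 2017 (Medicare), the end of 2018 (MarketScan) or March 31, 2020 (Optum). The plan supplies both code lists for this window. It does not give the changeover date, so the split of patients by coding system is unknown.

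**4. The flowchart step, reproduced (Section 5.3).**
- Optum: 4,297 − 33 = 4,264, as stated; 33/4,297 = 0.77%.
- MarketScan: 6,369 − 31 = 6,338, as stated; 31/6,369 = 0.49%.
- Medicare: 8,539 − 139 = 8,400, as stated; 139/8,539 = 1.63%.
- Total removed: 33 + 31 + 139 = 203. Before the step: 4,297 + 6,369 + 8,539 = 19,205. After it: 4,264 + 6,338 + 8,400 = 19,002.
- 203/19,205 = 1.06%; 203/19,002 = 1.07%.

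The 203 also include anemia, heparin-induced thrombocytopenia, stage 4, stage 5, ESRD and renal failure. The number removed on N18.9x alone lies between 0 and 203, and the documents cannot narrow that range.

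**5. Effect on power, at the ceiling.** Section 10 gives a pooled power of 0.9652 from 7,140 × 13.74/1,000 = 98.10 events. This is reproduced by Φ(√(98.10/4) × ln(1.8/0.84) − 1.96) = 0.965. If all 203 re-entered and all were matched, which cannot happen because many would still be excluded for other reasons, then 7,343 × 13.74/1,000 = 100.89 events and the same formula gives 0.969. Power is not the issue.

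**6. CKD in the matched cohort (Appendix B, PS-matched table, pooled).** Warfarin 170/3,570 = 4.8%; apixaban 176/3,570 = 4.9%; the tabulated standardized difference is 0.00.

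**The case against.** The strongest reply has three parts.

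First, the operative ICD-10 lists are said to be held outside the document, so the printed list may not be what was run. That does not dispose of the point: both lists for this criterion are printed in Appendix A, and N18.9x is written out with its label. If the program used something else, the plan needs correcting anyway.

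Second, widening the ICD-9 side, or justifying a broader proxy, would also make the two lists agree. That is true of consistency alone. It would take both lists away from the trial's limits, so it does not meet Section 5.2.2 as well as deletion does.

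Third, the effect is small and its size is not identified. This stands in full.

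A reader might go further and infer from Appendix B that the warfarin arm preferentially keeps unstaged CKD. In the unmatched table, total CKD ("Chronic kidney disease v2; n") exceeds the sum of stage 3-6 and stage 1-2 ("Chronic kidney disease Stage 1-2 (for PS); n") among warfarin users: 80 against 48 + 27 = 75 in Optum, and 76 against 56 + 18 = 74 in MarketScan. The documents do not support the inference, for these reasons:
- Neither table has a coding-era or index-year variable.
- Among apixaban users the staged counts exceed total CKD (90 + 28 = 118 against 116; 75 + 29 = 104 against 102). The categories therefore overlap or are not nested, and the subtraction cannot show that unstaged CKD is absent there.
- Unmatched Medicare cannot be used: its stage 1-2 cells read 0 and 0, while the matched table shows 28 and 27.
- Matched Medicare points the other way: warfarin 105 against 79 + 28 = 107; apixaban 124 against 92 + 27 = 119.

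Nor is the pre-matching standardized difference of 0.10 for chronic renal insufficiency without CKD a residual imbalance from this rule. By its label the variable leaves CKD out, and after matching its standardized differences are 0.04, 0.00 and −0.04 in the three databases.

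**Conclusion.** The mismatch is definite and can be read directly from Appendix A: unspecified CKD excludes a patient under ICD-10 and not under ICD-9, and it does not indicate the renal limits being emulated. The consequence is minor. At most 203 patients, about 1.1% of the cohort, were removed at the merged step, and the share due to N18.9x is unknown and may be close to zero. No direction of bias between arms can be established, and CKD is balanced among the matched patients.

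The conclusion assumes that the printed lists are the ones applied and that patients were coded under both systems during the entry window. The plan implies the second by supplying both lists but does not quantify it. This is a low-priority correction, worth making because it is cheap and unambiguous.

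**What to change.** - Delete N18.9x from the ICD-10 list, so that both lists mean stage 4, stage 5, ESRD or renal failure. Make the same change in the external code list.
- Re-run exclusion # 18 and the propensity score match, and update the flowchart and Appendix B.
- Report # 18 on its own flowchart line, apart from # 17 and # 22, so that its size can be seen.
- Leave unspecified CKD to the CKD covariates already in Appendix B. Confirm that at least one covariate entering the propensity score captures CKD without a stage, because the CKD rows marked for the propensity score are by stage and the definition of the overall CKD row is not given.
- If the sponsor means to keep the broader ICD-10 rule, the plan should say why and make the ICD-9 list agree.

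The cost is one code and one re-run. A few patients with unstaged CKD re-enter, and the number cannot exceed 203. Section 13 shows no comparative analysis date, so on the face of the document the change can be made before outcomes are compared by arm.

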# Appendix A

|                                    |                                                                                                                                                                                                                                                                                                                                                                                                                                                                          |
|------------------------------------|--------------------------------------------------------------------------------------------------------------------------------------------------------------------------------------------------------------------------------------------------------------------------------------------------------------------------------------------------------------------------------------------------------------------------------------------------------------------------|
| Trial ID                    |                                                                                                                                                                                                                                                                                                                                                                                                                                                                          |
| Trial Name (with web links) | AMPLIFY                                                                                                                                                                                                                                                                                                                                                                                                                                                  |
| Trial Name (with pdf links) |                                                                                                                                                                                                                                                                                                                                                                                                                                                                          |
| NCT                         | NCT00643201                                                                                                                                                                                                                                                                                                                                                                                                                                              |
| Therapeutic Area            | Cardiology/Vascular Diseases                                                                                                                                                                                                                                                                                                                                                                                                                                             |
| Brand Name                  | Eliquis                                                                                                                                                                                                                                                                                                                                                                                                                                                                  |
| Generic Name                | Apixaban                                                                                                                                                                                                                                                                                                                                                                                                                                                                 |
| Sponsor                     | Bristol-Myers Squibb                                                                                                                                                                                                                                                                                                                                                                                                                                                     |
| Year                        | 2013                                                                                                                                                                                                                                                                                                                                                                                                                                                                     |
| Measurable endpoint         | Percentage of Participants With Symptomatic Recurrent Venous Thromboembolism [VTE] (i.e. the Composite of Recurrent Deep Vein Thrombosis [DVT] or Fatal or Non-fatal Pulmonary Embolism [PE]) Until the Intended End of Study Treatment                                                                                                                                                                                                                                  |
| Exposure                    | Apixaban                                                                                                                                                                                                                                                                                                                                                                                                                                                                 |
| Comparator                  | Enoxaparin, Warfarin                                                                                                                                                                                                                                                                                                                                                                                                                                                     |
| Population                  |                                                                                                                                                                                                                                                                                                                                                                                                                                                                          |
| Trial finding               | HR = 0.84 (95%CI 0.60–1.18)                                                                                                                                                                                                                                                                                                                                                                                                                                              |
| Notes                       |                                                                                                                                                                                                                                                                                                                                                                                                                                                                          |
| No. of Patients             | 5,395                                                                                                                                                                                                                                                                                                                                                                                                                                                                    |
| Non-inferiority margin      | HR = 1.8                                                                                                                                                                                                                                                                                                                                                                                                                                                                 |
| Assay Sens. Endpoint        |                                                                                                                                                                                                                                                                                                                                                                                                                                                                          |
| Assay Sens. Finding         |                                                                                                                                                                                                                                                                                                                                                                                                                                                                          |
| Power                       | 0.90; With the use of an estimated incidence of the primary efficacy outcome of 3% at 6 months with conventional therapy and a noninferiority margin of 1.80 for the relative risk, we calculated that we would need to enroll 4094 patients for the study to have 90% power to show the noninferiority of apixaban, at a one-sided alpha level of 0.025. This sample was increased to 4816 patients to account for up to 15% of patients discontinuing treatment early. |

